1 PROTOCOL SUMMARY

1.1 SYNOPSIS

Title:	Dyslipidemia and Diabetic Retinopathy
Study Description:	Measurement of acid sphingomyelinase (ASM) activity in myeloid angiogenic cells
Objectives:	Determine if myeloid angiogenic cells isolated from diabetics with diabetic retinopathy have higher levels of ASM than age matched controls
Endpoints:	N/A
Study Population:	Diabetics and Age matched controls
Phase:	N/A
Description of Study Intervention:	N/A
Study Duration:	N/A
Subject Duration:	N/A

2 INTRODUCTION

Study Rationale The purpose of this study is to determine if hematopoietic reparative cells are defective in individuals with diabetes. Diabetic retinopathy (DR) is an eye disease related to diabetes. It can cause blurred vision and possible bleeding from the blood vessels in the back of the eye (retina). Damage to the cells of the blood vessels from DR can initiate pathology that then may cause vision loss or blindness. Even with current treatments, the quality of life for people with DR is much reduced.

Overall, this proposal will address the novel concept that the diabetes-induced decreases in DHA, and associated endothelial- specific increase in the central enzyme in sphingolipid metabolism ASM, affects both retinal endothelial cells and bone marrow-derived EPCs. Understanding both mechanisms of damage and repair have the potential to lead to therapeutic strategies that will address the dyslipidemia observed in diabetic retinopathy and may ultimately lead to the prevention of diabetes-induced retinal damage.

3 STUDY DESIGN

3.1 OVERALL DESIGN

Peripheral blood (200 cc) is removed from diabetics with and without diabetic retinopathy. Blood sampling is done in the AM between 8-10 due to circadian variation in bone marrow cell release.

3.2 END OF STUDY DEFINITION

N/A

4 STUDY POPULATION

4.1 INCLUSION CRITERIA

1. **Able to understand and sign an informed consent and HIPAA privacy document.**
2. **18 years of age or older at the time of informed consent**
3. **Able and willing to follow protocol instructions.**
4. **Presence of diabetic retinopathy by history, eye examination or by chart review.**

4.2 EXCLUSION CRITERIA

1. **Current use of tobacco products.**
2. **Use of medication other than prescribed antidiabetic agents.**

3. **Other ocular disease**
4. **Medical history of psychiatric illness.**
5. **Illicit drug use and drug addictions.**

Insert text>

4.3 SCREEN FAILURES

N/A

4.4 STRATEGIES FOR RECRUITMENT AND RETENTION

Clinic subjects will be recruited.

4.5 ADVERSE EVENTS AND SERIOUS ADVERSE EVENTS

There is minimal risk with a single blood draw and only infrequently is pain, bruising or infection at the site of the blood draw experienced. Occasionally a patient may feel faint during the blood draw and if this is the case, the patient will remain sitting for approximately 10 minutes until faint feeling dissipates.

5 STATISTICAL CONSIDERATIONS

5.1 STATISTICAL HYPOTHESES AND ANALYSIS

Diabetic individuals with diabetic retinopathy and age and gender matched controls were enrolled and CD34+ cells were isolated, and levels of ASM determined. All analyses were performed in GraphPad Prism v9.1 software. Prior to hypothesis testing, data were assessed for outliers, as indicated by the ROUT method, and outliers excluded from further analyses. Data underwent assessment for adherence to a normal (Gaussian) distribution using the Shapiro-Wilks Normality test. Data which were found to be normally distributed were analyzed by an unpaired Student's t-test (categorical predictor with 2 levels). For all statistical analyses, each input measure was indicative of a single, independent sample from one human subject. All data was analyzed at $\alpha=0.05$.

There have been 4 publications from this study.

Cholesterol crystal formation is a unifying pathogenic mechanism in the development of diabetic retinopathy. Hammer SS, Dorweiler TF, McFarland D, Adu-Agyeiwaah Y, Mast N, El-Darzi N, Fortmann SD, Nooti S, Agrawal DK, Pikuleva IA, Abela GS, [name], Busik JV. Diabetologia. 2023 Sep;66(9):1705-1718. doi: 10.1007/s00125-023-05949-w. Epub 2023 Jun 14. PMID: 37311879

Intravitreal Administration of AAV2-SIRT1 Reverses Diabetic Retinopathy in a Mouse Model of Type 2 Diabetes. Adu-Agyeiwaah Y, Vieira CP, Asare-Bediako B, Li Calzi S, DuPont M, Floyd J, Boye S, Chiodo V, Busik JV, [name]. Transl Vis Sci Technol. 2023 Apr 3;12(4):20. doi: 10.1167/tvst.12.4.20. PMID: 37070938.

Lipids, hyperreflective crystalline deposits and diabetic retinopathy: potential systemic and retinal-specific effect of lipid lowering therapies. Jenkins AJ, [name], Busik JV. *Diabetologia*. 2022 Apr;65(4):587-603. doi: 10.1007/s00125-022-05655-z. Epub 2022 Feb 11. PMID: 35149880

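### Does the analysis of CD34+ cells leave the objective about myeloid angiogenic cells untested?

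*Combined protocol and SAP*

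**What the plan says.** The synopsis in section 1.1 describes the study as "Measurement of acid sphingomyelinase (ASM) activity in myeloid angiogenic cells". Its only objective is to find out whether "myeloid angiogenic cells isolated from diabetics with diabetic retinopathy have higher levels of ASM than age matched controls". The endpoint entry reads N/A, so no separate endpoint definition names the cells or the assay.

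Section 2 (Introduction) uses broader language. The study is meant to "determine if hematopoietic reparative cells are defective in individuals with diabetes", and the closing paragraph of that section refers to bone marrow-derived EPCs, an abbreviation it does not expand.

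Section 3.1 describes only the sampling: "Peripheral blood (200 cc) is removed from diabetics with and without diabetic retinopathy". It adds a morning time window, justified by the daily rhythm of cell release from the marrow. It gives no isolation step.

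Section 5.1, the only analysis text, states "CD34+ cells were isolated, and levels of ASM determined" and then describes outlier screening, a normality check and an unpaired t-test at a significance level of 0.05. It is written in the past tense and adds "There have been 4 publications from this study".

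**The concern.** The cell population is part of the definition of the outcome. If an objective names one population and the analysis uses another, the test may be valid and still answer a different question. Here the name in the objective appears only in section 1.1 and the name in the analysis only in section 5.1. The sections between them add further names instead of connecting the two.

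The readout is also loosely worded. The study description speaks of ASM activity, while the objective and the analysis speak of levels. No assay or unit shows whether that means enzyme activity or amount of protein.

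At stake would be the reach of the only conclusion the study offers. A difference found in CD34+ cells would not by itself support a statement about some other cell type. Because section 5.1 was written after the analysis, rewording the objective now to fit the assay could also make a later choice look planned.

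**Working it through.** No arithmetic applies. The documents give no sample size, effect size, standard deviation or power figure, and the question is one of wording. The check is to set every mention of the cells side by side.

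| Place | Name used for the cells | Marker or source given | ASM readout |
|---|---|---|---|
| 1.1, study description | myeloid angiogenic cells | none | activity |
| 1.1, objective | myeloid angiogenic cells | none | levels |
| 1.1, endpoints | N/A | N/A | N/A |
| 2, opening sentence | hematopoietic reparative cells | none | none |
| 2, closing paragraph | bone marrow-derived EPCs | bone marrow origin | none for a measurement |
| 3.1 | no name; release of bone marrow cells is mentioned | peripheral blood, 200 cc | none |
| 5.1 | CD34+ cells | CD34 | levels |

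**Count.** There are four names across the document, no sentence linking any two of them, and one name (CD34+) that carries a marker. For ASM there is one mention of activity, two of levels, and no assay or unit.

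**Do the sections contradict each other?** A contradiction needs evidence that the names denote different cells. The table contains none. Sections 2 and 3.1 point to one broad idea: reparative cells of bone marrow origin, sampled from circulating blood. That context fits the names being used interchangeably. It does not prove that they are equivalent.

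**Could an analyst go wrong by following the text?** Section 4.5 refers to a single blood draw. Section 5.1 describes one isolation, one ASM measurement and one two-group test, with one independent value per subject. No second fraction is described, so nobody has to choose between two sets of data.

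**What would each reading change?**

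- *The names mean the same preparation.* The objective, the data and the test already match. Only a linking sentence is absent.
- *The names mean different cells.* The values, the test and the p-value are the same as before. The conclusion would then have to be confined to CD34+ cells, which is how section 5.1 already labels them.

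**Activity or levels.** The objective and the analysis use the same word. The odd one out is a single word in the descriptive line of the synopsis. The missing unit is a gap in reporting, and it affects both groups alike.

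**Timing.** The risk of a silent retrospective edit arises only if the objective is actually rewritten. A statement that the CD34+ cells are the cells meant in the objective would alter nothing that was tested. The publication count adds little, because none of the titles listed in section 5.1 mentions ASM or either cell name.

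**The case for a change.** The strongest case for action is that this is a study with one objective and one comparison, and the reader is never told that the second answers the first. With endpoints entered as N/A, no other part of the document fixes what was measured or in which cells. The defect can be verified from two sections, and a remedy would need no new data. If the cells are equivalent, one sentence settles the matter. If they are not, the stated objective was not the one tested and readers should be told.

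Much of this stands as description. The link is unstated, the name in the objective has no marker, and the readout has no unit. The step from there to a flaw in the plan does not hold. The serious branch depends on the two names covering different cells, and the documents do not show that they do. It is also too strong to say that neither population is defined, since CD34+ is itself a designation by marker. What remains is a request for detail, and the cheapness of supplying it does not show that its absence harms the analysis.

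**Conclusion.** No change to the plan follows. Sections 1.1 and 5.1 name the assayed cells differently without linking the names. This is an unstated connection, not a demonstrated mismatch. Its numerical size is zero: no estimate, test, significance level or sample size depends on which name is used. The practical consequence is limited to labelling, and a careful reader or author handles it by describing the result as one for CD34+ cells from peripheral blood and by giving the ASM unit.

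The conclusion rests on two assumptions. The first is that section 5.1 correctly describes what was isolated and assayed. The second is that no separate myeloid angiogenic cell fraction was prepared, and the documents mention none. If such a fraction did exist, or if the sponsor regards the two names as different cells, the conclusion would need to be limited to the cells actually assayed, and any restated objective would need to be disclosed as made after the analysis. Nothing in the text points that way.

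### ROUT-flagged ASM values, and with them subjects, are dropped before the normality check and the t-test, with no assay-fault condition or all-values analysis documented; the harm depends on skew, group size, Q and ROUT mode, none of which is stated

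*Combined protocol and SAP*

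**What the plan says.** Everything on this point is in section 5.1 (Statistical hypotheses and analysis), apart from the objective in the synopsis (section 1.1).

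- **Exclusion:** "Prior to hypothesis testing, data were assessed for outliers, as indicated by the ROUT method, and outliers excluded from further analyses".
- **Normality check, described next:** "Data underwent assessment for adherence to a normal (Gaussian) distribution using the Shapiro-Wilks Normality test".
- **Test:** "Data which were found to be normally distributed were analyzed by an unpaired" Student's t-test, at alpha 0.05. Sidedness is not given, and no test is named for data that fail the check.
- **Unit of analysis:** "each input measure was indicative of a single, independent sample from one human subject".
- **Software:** "All analyses were performed in GraphPad Prism v9.1 software". No ROUT settings are recorded.
- **Objective:** "Determine if myeloid angiogenic cells isolated from diabetics with diabetic retinopathy have higher levels of ASM than age matched controls".

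The documents give no group size, ASM distribution, Q, ROUT mode, number excluded, laboratory criterion for exclusion, or analysis that keeps all values.

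**The concern.** ROUT flags values that lie too far from a roughly Gaussian core. If ASM is right-skewed, genuine high values get flagged, and those are the values the objective is about. Three consequences are possible.

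1. Trimming each group's upper tail makes the groups look less variable than they are. The standard error is then too small, and a true null is rejected too often.
2. If ROUT is run on both groups together, a genuinely higher retinopathy group loses more of its values, and the estimated difference shrinks.
3. Because exclusion comes before the Shapiro-Wilk check, trimming helps decide whether the t-test applies at all.

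Without Q, the mode and the counts removed, a reader cannot tell whether the reported comparison carries inflated error, a shrunken difference, or neither.

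**Working it through.** **Inputs from the documents.** Alpha 0.05; the order ROUT, then Shapiro-Wilk, then unpaired t-test; one value per subject. There is no power or sample-size figure to reproduce.

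**Assumptions, not in the documents.** Equal groups of n = 6, 10 or 20; two-sided tests; Q = 1% unless stated; control ASM = exp(σZ) with Z standard normal and log-SD σ = 0.5, 0.8 or 1.0, which is a coefficient of variation √(exp(σ²) − 1) of about 53%, 95% or 131%. The t-test is used if both groups pass Shapiro-Wilk (p > 0.05) after exclusion; otherwise exact Mann-Whitney on the trimmed data.

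**ROUT as simulated.** Lorentzian robust location; robust SD = 68.27th percentile of absolute residuals × N/(N − 1); t-based p-values; false-discovery step at Q on the largest 30% of residuals. There were 20,000 trials per scenario (10,000 for other Q). The Monte Carlo SE of the whole-sequence null rates is at most 0.004.

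**1. Null rejection, whole sequence, per-group ROUT, Q = 1%**

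| log-SD | n = 6 | n = 10 | n = 20 |
|---|---|---|---|
| 0.5 | 0.054 | 0.073 | 0.084 |
| 0.8 | 0.058 | 0.094 | 0.112 |
| 1.0 | 0.059 | 0.107 | 0.128 |

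Over the same grid:
- no exclusion: 0.042 to 0.054
- pooled ROUT: 0.046 to 0.055
- per-group ROUT at Q = 0.1%: 0.053 to 0.101
- per-group ROUT at Q = 5%: 0.063 to 0.161

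The largest ratio to nominal is 0.128/0.05 ≈ 2.6 at Q = 1% and 0.161/0.05 ≈ 3.2 at Q = 5%.

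**2. Little or no skew, Q = 1%, per group.** Normal data give 0.051 to 0.053, against 0.050 to 0.051 with no exclusion. At log-SD 0.25 (coefficient of variation about 25%) repeated runs gave 0.049 to 0.066. The highest value, at n = 20, compares with 0.059 without exclusion in the same run: 0.066 − 0.059 = 0.007, with an SE of about 0.005 on each rate.

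**3. Effect on the normality check, per-group ROUT.** Share of null data sets in which both groups pass, before and after exclusion:
- log-SD 0.5: 57% to 71% (n = 10); 23% to 43% (n = 20)
- log-SD 0.8: 28% to 54% (n = 10); 3% to 18% (n = 20)

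Among the sets that pass, the t-test rejects at these rates (log-SD 0.5 / 0.8):
- n = 10: 0.081 / 0.117 after exclusion; 0.062 / 0.082 without
- n = 20: 0.108 / 0.193 after exclusion; 0.075 / 0.112 without

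Part of this excess therefore comes from the normality gate itself, not from ROUT.

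**4. True shift of 1 log-SD (geometric-mean ratio exp(σ): 1.65 at 0.5, 2.23 at 0.8), n = 20**

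| Mode, log-SD | Cases removed | Controls removed | Fall in mean difference | Power, all values to ROUT |
|---|---|---|---|---|
| Pooled, 0.5 | 4.8% | 0.4% | 18% | 85% to 81% |
| Pooled, 0.8 | 12.9% | 1.7% | 44% | 85% to 73% |
| Per group, 0.8 | 5.1% | 5.1% | 15% | 85%, unchanged |

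At n = 10, pooled ROUT lowers the difference by 16% (log-SD 0.5) and 40% (log-SD 0.8).

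**5. The unstated mode by itself.** Switching between per-group and pooled ROUT changes the null verdict in 3.1%, 6.0% and 7.7% of trials at n = 20 (log-SD 0.5, 0.8, 1.0).

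**The case against.** **The fallback test is supplied here.** Section 5.1 names only the t-test. Passing the check and rejecting with that test alone occurs in 0.058 / 0.063 of null trials at n = 10 and 0.046 / 0.035 at n = 20 (log-SD 0.5 / 0.8). At n = 20, log-SD 0.8, the fallback contributes (0.112 − 0.035)/0.112 ≈ 69% of the whole-sequence rate. This stands as a limit: the whole-sequence figures depend on the assumed Mann-Whitney. It does not remove the point, because among data sets that reach the t-test, exclusion still raises the error above what the gate alone produces.

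**Skew is not shown.** This also stands. No ASM distribution is given, and with mild skew the effect is small.

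**The harms are alternatives.** Per-group ROUT inflates error but did not cost power in the case examined; pooled ROUT holds the error but shrinks the difference. They must not be added together.

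**Silence is not proof.** The document is short and section 5.1 is in the past tense. A reader might infer that no assay checks were made, or that no all-values result exists. The text supports only that neither is documented.

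**Conclusion.** The point holds in conditional form. The exclusion rule is stated outright. That it precedes the normality check follows from the sentence order and from excluded values leaving all further analyses.

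Under marked right skew, following the rule can make the result worse, and the unstated mode decides how: excess false positives if per group, an attenuated difference if pooled. The sizes rest on lognormal data, equal groups, two-sided tests and an assumed fallback. No single multiple of 0.05 bounds the inflation, because Q is unstated too.

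A reader might infer that this study's finding is a false positive, or that retinopathy cases were in fact removed selectively. The documents support neither: they give no data, group sizes or exclusion counts. This is a cheap improvement to analysis and reporting, not a demonstrated error in the result.

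**What to change.** - **Main result:** compare all subjects with a valid assay, using one method fixed without looking at the skew of the data. Either Mann-Whitney, or a t-test on log ASM, which estimates a ratio of geometric means. Choosing between them after seeing the skew would bring back a data-dependent test choice.
- **Exclusions:** only for a documented technical failure, such as a failed assay control, judged without knowledge of group where that is still possible.
- **ROUT:** show the ROUT-excluded result only as a labelled sensitivity analysis, with Q, mode and number excluded per group.
- **Minimum:** since section 5.1 reports work already done, add the all-values result beside the existing one and disclose Q, mode and exclusions by group.

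Under the lognormal nulls above, all-values Mann-Whitney rejects at 0.039 to 0.050 and the log-scale t-test at 0.049 to 0.053. Their power at log-SD 0.8, n = 20 and a 1 log-SD shift is 85% and 87%.

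**Cost:** a wording change and one rerun, provided the individual ASM values were kept; no new subjects or assays. The p-value may become less favourable, Mann-Whitney is slightly conservative in very small groups (0.039 to 0.042 at 6 per group), and the log scale changes the estimand.

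### Controls matched on age and gender are compared by an unpaired t-test that ignores both factors; if either relates to ASM, the test is conservative and precision is lost

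*Combined protocol and SAP*

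**What the plan says.** Section 5.1 describes the design in one sentence: "Diabetic individuals with diabetic retinopathy and age and gender matched controls were enrolled". The same paragraph gives the analysis: "Data which were found to be normally distributed were analyzed by an unpaired" Student's t-test, with the predictor described as "categorical predictor with 2 levels". It is the only test of the group difference that the documents name. It serves the only objective in the synopsis (section 1.1), which is whether cells from patients with retinopathy "have higher levels of ASM than age matched controls".

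Section 5.1 adds that "each input measure was indicative of a single, independent sample from one human subject". The documents mention no covariate, stratum, matched-set term or paired test.

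The matching itself is described differently from place to place. The synopsis gives the population as "Diabetics and Age matched controls", with no mention of gender. Section 3.1 says only that blood "is removed from diabetics with and without diabetic retinopathy" and does not mention matching.

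**The concern.** Matching makes the groups alike on age and gender, so chance differences in those factors no longer add to the difference in mean ASM. An unpaired t-test does not know this. It estimates its standard error from the whole within-group spread, including any part due to age and gender, as if the groups had been sampled freely.

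If age or gender relates to ASM, three things follow: the confidence interval is wider than it need be, the t-test's true type I error is below the stated 0.05, and a real difference is more easily missed. The design pays for the matching and the analysis discards the gain.

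The sentence about single, independent samples does not settle this. It rules out repeated measurements on one person; it does not bring age or gender into the analysis.

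**Working it through.** **Inputs.** From section 5.1: α = 0.05, matching on age and gender, two groups, group as sole predictor. No sample size, SD, effect size or power is stated, so there is no figure of the plan's own to reproduce. Assumed: two-sided testing, equal groups of n = 5, 10 or 20, and R² (the share of within-group ASM variance explained by age and gender jointly) from 0 to 0.5.

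**Step 1: standard error.** With within-group variance σ² and groups balanced on age and gender:

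- true variance of the mean difference = 2σ²(1 − R²)/n
- variance used by the unpaired t-test = 2σ²/n
- overstatement of the standard error = 1/√(1 − R²)

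At R² = 0.3 this is 1/√0.7 = 1.195, or 20% too large. The result needs balance, not pairs, so it applies to individual and frequency matching alike. For 1:1 pairs the within-pair correlation takes the place of R².

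**Step 2: type I error and power of the t-test.** The large-sample type I error is 2[1 − Φ(1.96/√(1 − R²))], which gives 0.050, 0.039, 0.028, 0.019 and 0.006 at R² = 0, 0.1, 0.2, 0.3 and 0.5. Simulation gives the finite-sample values. Power is for an effect at which the model with age and gender has 80%.

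| R² | SE overstated | Type I error, n = 20 | Type I error, n = 10 | Power, n = 20 | Power, n = 10 | Power, n = 5 |
|---|---|---|---|---|---|---|
| 0 | 0% | 5.0% | 5.0% | 80% | 81% | 84% |
| 0.1 | 5% | 3.9% | 4.0% | 77% | 77% | 81% |
| 0.2 | 12% | 2.9% | 3.1% | 73% | 73% | 77% |
| 0.3 | 20% | 2.0% | 2.2% | 68% | 68% | 72% |
| 0.5 | 41% | 0.7% | 0.9% | 52% | 52% | 57% |

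The model with age and gender holds its type I error at about 5% throughout. Frequency matching, simulated separately at n = 20, gives 3.9%, 2.1% and 0.7% for the t-test at R² = 0.1, 0.3 and 0.5, in line with the table.

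**Step 3: when an alternative pays.** The alternative gives the narrower interval once R² (or, for pairs, the within-pair correlation) exceeds 1 − (t_unpaired/t_alternative)², where each t is the two-sided 5% critical value. The degrees of freedom are 2n − 2 (unpaired), 2n − 4 (two covariates) and n − 1 (paired).

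| n per group | t unpaired | t covariate | t paired | Break-even R², covariate | Break-even correlation, paired |
|---|---|---|---|---|---|
| 20 | 2.024 | 2.028 | 2.093 | 0.004 | 0.06 |
| 10 | 2.101 | 2.120 | 2.262 | 0.02 | 0.14 |
| 5 | 2.306 | 2.447 | 2.776 | 0.11 | 0.31 |

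**Step 4: inexact matching.** Suppose all of R² comes from age and a fraction f of the age variance remains in the group difference. The overstatement becomes 1/√(1 − R²(1 − f)). If matched ages differ uniformly by up to 1 SD, the difference has variance 1/3 against 2 when unmatched, so f = 1/6. Up to 1.5 SD, f = 0.75/2 = 0.375. At R² = 0.3 the overstatement falls from 20% to 15% and 11%. It shrinks but keeps its sign.

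**The case against.** The strongest objection is that everything depends on a relation the documents never assert. They do not say that ASM varies with age or gender. At R² = 0 the t-test is correct; at R² = 0.1 with 20 per group it loses three points of power; with 5 per group adjustment does not pay until R² is about 0.1. The large figures need R² = 0.5, which the documents do not support. The error is also conservative, so it cannot undermine a positive result. All of this stands: it limits the size of the point but not its direction.

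A second objection is that the independence sentence fits group-level matching followed by a two-sample test. It does, but balance alone produces the overstatement, so the point does not need individual pairs.

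Third, 1/√(1 − R²) assumes close balance, and no matching tolerance is stated. That is fair: the factor is an upper limit, as the inexact-matching calculation shows.

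Fourth, section 5.1 removes outliers by ROUT before testing, with no Q stated, and this can push type I error the other way. In an approximate simulation with 10 per group and R² = 0.1, type I error was 4.0% without removal, 4.2% at Q = 1% and 5.3% at Q = 10%. At R² = 0.3 it stayed below 5% (2.3% at Q = 1%, 3.4% at Q = 10%). So the statement that type I error is below 0.05 is about the t-test itself; with small R² and aggressive outlier removal the whole procedure may not be conservative. The lost precision remains.

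**Conclusion.** The concern holds. The design controls age and gender and the only named group comparison ignores them. The direction is certain for the t-test: correct if neither factor relates to ASM, conservative and less precise if either does. The size is not known from the documents. Under the assumed range the standard error is overstated by 0% to 41%, and at 10 or 20 per group the t-test's power is about 80% down to 52% where the adjusted model has 80%.

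This is worth correcting because the correction is cheap, not because a reported positive finding is in doubt. A null or imprecise result is where it would matter most. The differing descriptions of the matching are a separate reporting gap and add nothing to the weight of this point.

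**What to change.** Fit a linear model of ASM on group with age and gender as covariates, and report the adjusted difference with its 95% confidence interval. Section 5.1 reports that "There have been 4 publications from this study", so label the reanalysis post hoc and keep the original t-test beside it. If controls were matched individually and the set identifiers survive, a paired test or a mixed model with a matched-set term is an alternative, but should not be the default in small samples. While revising the text, state whether matching was individual or by frequency, the ratio and the factors, and reconcile sections 1.1 and 5.1.

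The cost is one reanalysis with variables that the matching already required, provided age and gender can still be linked to each ASM value. The statistical downside arises if R² = 0. Where the t-test has 80% power, the covariate model then has 79.9%, 79.4% and 76% at 20, 10 and 5 per group, and slightly less if matching is inexact. The paired t-test has 78%, 75% and 67%, which is why the covariate model is preferred.
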